1.1 Objective

Stroke is a significant cause of morbidity, mortality, and loss of independence worldwide. In Denmark 12,000 people have a stroke per year. About one fourth of patients admitted with a stroke have had previous strokes or TIA. The risk of recurrent stroke is highest in the first weeks and decreasing with time.

Hypertension is one of the leading risk factors for vascular diseases, including stroke and TIA, and lowering of the blood pressure is therefore an essential part of stroke treatment. Smoking cessation, physical activity, and adherence to antihypertensive and antithrombotic medication is highly recommended in patients with minor stroke and TIA.

The objectives of this study are 1) to test the feasibility of a lifestyle and behavioural intervention in a clinical setting, and 2) to test the effect of the intervention on blood pressure in patients with minor stroke and TIA.

1.2 Target and study population

The study will include patients with acute minor stroke or TIA who are discharged to their own home. Patients with prior disability, severe communication problems, severe psychiatric disease, or alcohol abuse will be excluded.

1.3 Methods

1.3.1 Study design

The study will be a randomized controlled feasibility trial. Participants (n=40) will be randomly allocated to either an early initiated counselling intervention with frequent follow-up sessions in 12 weeks, or usual care.

1.3.2 Exposures and outcomes of interest

Participation rate and adherence to the treatment program will be the primary outcome measures of feasibility. Systolic blood pressure will be the primary outcome measure of effect.

1.3.3 Recruitment

Participants will be recruited from admissions to the Department of Neurology at Nordsjællands Hospital, Hillerød.

1.3.4 Statistical analyses

Student t-test will be used as significance test for differences in blood pressure between the treatment groups.

1.4 Expected results

We expect to estimate the participation rate and variance of the blood pressure. These estimates will be used in planning a future randomized controlled trial.

1.5 Discussion

The greatest challenge will be the participation and retention of the participants throughout the study period.

2 Background

Stroke is a significant cause of morbidity, mortality, and disability, both in western countries and globally (1). In Denmark the incidence is around 12,000 per year (2). The life expectancy of patients with stroke and transient ischemic attacks has increased during the last few decades. As a consequence of this the risk of recurrent stroke and other cardiovascular disease has increased. Interventions to reduce the risk of stroke recurrence are therefore needed.

Approximately one in four patients with stroke have recurrent stroke. The risk of recurrent stroke is greatest closest to the incident stroke. Within the first year 12-13 percent have recurrent stroke and after the first year the recurrence rate is 5-6 percent per year (3). Recurrent stroke is an independent risk factor for loss of function, institutionalization, and death (4).

The most important risk factor for stroke is arterial hypertension. Not only does it increase the risk of stroke considerably, it is also highly prevalent in the general population. Other lifestyle factors, such as smoking, physical inactivity, unhealthy eating habits, and abdominal obesity also contribute to the risk of stroke (5).

Preventive medication is an important part of the secondary and tertiary prevention in patients with stroke and TIA. Most of the patients get prescriptions for antithrombotic drugs or drugs to reduce their blood pressure or blood lipids (6). Several studies have found that a substantial part of the patients discontinue the drug treatment over time (7).

2.1 Literature review

Previous research has attempted in different ways to change health behaviour with the aim of preventing recurrent strokes and other cardiovascular diseases in stroke survivors.

The results of previous studies have been varying and it is therefore difficult to point out any specific interventions or element of interventions which would be feasible to implement in clinical practice. Lawrence *et al.* (8) found in a systematic review of 20 randomized controlled trials that multimodal behavioural interventions had a beneficial effect on especially blood pressure. In a similar study Deijle *et al.* (9) found that lifestyle interventions had greater effect if the intervention contained elements of physical activity. On the contrary Lager *et al.* (10) found in a systematic review of 26 randomized controlled trials that interventions aiming at reducing the risk of cardiovascular events in stroke patients had no significant effect.

The time of inclusion in the previous studies has varied quite a lot. In some studies the participants were included within 1-2 weeks after the stroke and in others participants were included until almost two years after. It has been hypothesised in other patient groups that the time just after the diagnosis constitutes a certain *window of opportunity*; a limited period of time in which the patient is particularly receptive of information and behavioural changes (11).

2.2 Justification

In the last decades there has been an increased focus on the importance of health behaviour in the public and among patients in relations to prevention of vascular diseases. There is solid scientific evidence of the harmful effects of lifestyle factors, such as smoking, physical inactivity, and alcohol overuse. But we still lack knowledge about how to disseminate this evidence to the public and how to help and support patients in making suitable choices to prevent recurrence and progression of their disease.

A particularly perspective in this context is the considerable increase of the stroke burden we have seen in low- and middle income countries, which is attributional to the changes in life expectancy, life style, and living conditions. Previously stroke and other vascular diseases were considered diseases of

affluence; now 75 percent of all strokes occur in low- and middle income countries. This change from infectious diseases being the primary burden to non-communicable diseases is in many ways positive, but is also a great challenge. We need to focus our research on treatments which are effective and inexpensive.

2.3 Relevance

This study will contribute with new knowledge about how patient counselling can be conducted in clinical practise and its effect on the patients' risk of recurrent vascular disease after stroke or TIA. The intervention tested in the study will be implemented in current clinical practise and thereby have a direct effect in the secondary and tertiary prevention of strokes.

2.4 Feasibility

Each year the Department of Neurology at Nordsjællands Hospital admits approximately 650-700 patients with a confirm stroke and 200 patients with TIA. Of the patients with stroke 60-65% have a Scandinavian Stroke Scale between 45-58. It is therefore expected that around 600 patients each year will fulfil the inclusion criteria. It is uncertain how many of the patients will meet the exclusion criteria.

3 Purpose, Objectives and Hypothesis

3.1 Purpose of the study

The overall purpose of our research is to develop effective and clinically feasible interventions to prevent recurrent strokes in patients with minor stroke and transient ischemic attacks.

3.2 Objectives

The aim of this study is

- 1) to evaluate the feasibility of a client-centred patient counselling intervention focused on smoking cessation, physical activity, and adherence to preventive medication in patients with minor stroke and transient ischemic attack, and
- 2) to test the effect of that intervention on blood pressure and other cardiovascular risk factors in patients with minor stroke and transient ischemic attack.

3.3 Hypothesis

The hypothesis of the study is that early client-centred patient counselling with repeated follow-up sessions after discharge can reduce the blood pressure through smoking cessation, physical activity, and improved adherence to preventive medication in patients with minor stroke and transient ischemic attacks compared to simple encouragement to lifestyle change.

4 Populations

4.1 Study unit

The study unit will be individual patients.

4.2 Target population

The target population is hospitalized patients with recent minor stroke or transient ischemic attack, who are discharged to their own home, with only minor neurological deficits and do not require specialized rehabilitation.

4.3 Study population

We will include patients with acute minor stroke or TIA admitted to the Department of Neurology at Nordsjællands Hospital (n=40).

Inclusion criteria

- Male or female, age \geq 18 years old
- TIA (ICD-10 G45.9) or stroke (ICD-10 I61, I63, I64) with a Scandinavian Stroke Scale of 45-58.
Diagnosis must be confirmed by a neurologist
- Able to give a valid written consent

Exclusion criteria

- Severe barriers to communication
- Not able to use a telephone
- Severe disability prior to the stroke (WHO Performance Status >2; mobilised less than 50 % of the day)
- Active abuse of alcohol or narcotics
- Severe psychiatric illness (affective disease, dementia, schizophrenia, anxiety)

5 Study design

The study will be a parallel group randomized controlled feasibility trial. Participants will be randomly allocated to either usual care or a counselling intervention, with follow-up sessions post-discharge with 3-4 weeks intervals in 12 weeks.

Intervention

Participants in the intervention group will receive targeted counselling in lifestyle changes focusing on smoking cessation, everyday physical activity, and adherence to preventive medication. The primary aim of the initial counselling session will be to assess the participant's intentions and willingness to change behaviour, and to support the participant in establishing realistic goals. The participants will be encouraged to bring a relative or close friend to the initial counselling session, who can be a support for the participant after the discharge.

Ahead of the initial counselling session we will do a detailed assessment of the participant's lifestyle and physical condition; including an assessment of lung function and oxygen uptake.

After the participants are discharged from the hospital we will do 3-4 follow up counselling sessions. The aim of these sessions will be to re-evaluate the previous goals or to re-assess the participant's willingness to change if the participant continues to be ambivalent about lifestyle changes.

The participant's level of physical activity will be monitored from the discharge to the last follow up after 12 weeks. The participant will be handed out an activity tracker from the hospital which will record all movement day and night.

Usual care

Participants in the control group will receive the standard care, which include a review of prescribed medication, and both verbal and written encouragement of a healthy lifestyle.

[figure not shown]

Figure 1 Flowchart of recruitment, inclusion & allocation of participants

6 Recruitment

6.1 Sampling procedure

Potential candidates will be contacted by the investigator while they are in the hospital, usually within the first few days, and asked if they want to participate. Before inclusion a set of control questions are asked to evaluate eligibility and participation is approved by a neurologist.

Potential candidates are informed that participation is voluntary and that consent to participation can be withdrawn at any time. Participation or non-participation will not affect any other parts of the treatment.

6.1.1 Source of study units – Study population

Participants will be recruited from the Department of Neurology at Nordsjællands Hospital.

6.1.2 Inclusion/exclusion criteria for sampling

Patients will be eligible if they have one of the defining diagnoses, as confirmed by a clinical examination by a neurologist, and are adults and able to give a valid written consent.

To make the study more feasible we will have to exclude patients who are not likely to complete the intervention.

Verbal client-centred counselling is a significant part of the intervention and telephone counselling might be part of the follow-up. Therefore, patients will not be able to participate if they have severe communication barriers, such as aphasia, or are unable to use a telephone.

Patients with an active abuse of alcohol or narcotics will not be eligible to participate as they often will need a more intense type of intervention.

Motivation for physical activity is also a central part of the intervention and the participants must be able to be physically active by themselves. Therefore, we will not include patients who prior to the stroke were unable to walk freely or immobile due to other disabilities.

Patients with severe mental illness often have reduced self-efficacy believes and their ability to change lifestyle behaviour can therefore be limited. For these groups of patients a more intensive type of intervention might be needed. This is beyond the scope of this study, but will be treated in another part of the research program.

7 Data management

7.1 Variables

7.1.1 Outcome variables

Measures of feasibility

The primary outcome measure will be the rate of participation in the study; measured as:

- 1) the proportion of patients eligible for the study out of all patients with stroke admitted to the Department of Neurology,
- 2) the proportion of patients accepting to participate in the study, and
- 3) the degree of adherence to the intervention (proportion of attendance in follow-up sessions)

Aside from participation we will evaluate the participants' satisfaction with the overall intervention and single parts of the intervention.

Variable	Measure	Type/scale	Source
Admissions	Number of patients admitted in the study period	Continuous	
Eligibility	Number of patients who would be candidates for participation	Continuous	
Recruitment	Number of participants recruited	Continuous	
Adherence	Number of participants completing the treatment Degree of participation	Continuous	
Satisfaction	Five level Likert Scale	Ordinal	

Secondary outcome

Measure of effect

The secondary outcome measure will be arterial blood pressure measured 12 weeks after the start of the intervention. The arterial blood pressure will be measured as a continuous variable in mmHg. The participant should be sitting still and resting for ten minutes before the measurement. To avoid extreme values the measurement will be repeated three times with a few minutes apart and the median value will be used for the statistical analysis.

This outcome measure was chosen because hypertension is the most significant risk factor for stroke and TIA (5) and because previous studies have found that it might be possible to lower the blood pressure through lifestyle interventions (8).

Tertiary outcomes

Tertiary outcomes after 12 weeks will include:

Variable	Measure	Type/scale	Source
Changes in behavior			
Smoking	Daily; weekly; Rarely; Former; Never smoked	Categorical	B
Physical activity	Questionnaire	Ordinal	B
Adherence to medication	Questionnaire	Continuous	B
Anthropometric measures			
Body weight	Measured (kg)	Continuous	C
Height	Measured (cm)	Continuous	C
Waist + hip circumference	Measured (cm)	Continuous	C
Patient reported outcomes			
Fatigue	Questionnaire		B
Self-rated health	Two item questionnaire	Categorical	B

Secondary outcomes after one year will include:

Variable	Measure	Type/scale	Source
New stroke/TIA	Event + days till event	Categorical/time	A
Cardiac admission	Event + days till event	Categorical/time	A
Death	Event + days till event	Categorical/time	A

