7.1.2 Other variables

Baseline data

Before the participants are randomized following baseline data will be collected (*the brackets state the type of data*):

Variable	Measure	Type/scale	Source
Diagnosis	ICD-10; established through clinical exam/CAT scan	Categorical	A
Gender	Male/Female	Categorical	A
Birthdate		Date	A
Symptom onset		Date/time	A/B
Admission		Date/time	A
Living arrangement	Living alone; living with partner; care facility; other	Categorical	B
Performance status (prior)	WHO performance status	Ordinal	B
Self-rated health	Two item questionnaire	Ordinal	B
Alcohol consumption (/week)	Within/above recommended level (7/14 units/week)	Categorical	B
Smoking	Daily; weekly; Rarely; Former; Never smoked For current smokers the amount and type of tobacco is also recorded	Categorical	B
Physical activity		Ordinal	B
Comorbidities	Charlson's Comorbidity Index: Aggregated scale based on weighted scores of presence or non-presence different diseases Individual diseases or groups will be coded as Y/N and the CCI will be calculated from these	Ordinal	A/B
Body weight	Measured (kg)	Continuous	C
Height	Measured (cm)	Continuous	C
Waist + hip circumference	Measured (cm)	Continuous	C
Stroke severity	Scandinavian Stroke Scale; Sub-scores: Consciousness, eye palsy, arm palsy, hand palsy, leg palsy, orientation, speech (dysphasia), facial palsy, gait	Ordinal	C
Vital signs	Early Warning Score; Sub-scores: Respiration rate, oxygen saturation, heart rate, temperature, systolic/diastolic blood pressure, consciousness	Ordinal	C
Cardiac rhythm	ECG: Normal; arterial fibrillation; other arrhythmia	Categorical	C
Blood glucose	S-glucose at admission; HbA1c	Continuous	C
Blood lipids	Total cholesterol, LDL, VLDL, HDL, triglycerides	Continuous	C

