8.3 Statistical analysis

Hypothesis testing for the secondary outcome (systolic blood pressure) will be done as intention-to-treat (including all participants allocated) using a paired t-test comparing baseline systolic blood pressure with systolic blood pressure measured after 12 weeks. Results will be reported as mean difference of changes with 95 percent confidence intervals.

Tertiary outcome measures will be analyzed as intention-to-treat using unpaired student t-test for continuous variables and either chi-squared test or fisher's exact test for categorical variables. Treatment allocation will be blinded to the investigator.

Statistical analyses will be done in R 3.3.1/R Studio 0.99. A significance level of 5 percent will be considered statistically significant.

9 Validity and bias

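### The 12-week smoking outcome is five-category status in all participants, a diluted and noisy measure of cessation, and no analysis of quitting among baseline smokers is specified

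*Combined protocol and SAP*

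**What the plan says.** Section 3.3 hypothesises that the counselling "can reduce the blood pressure through smoking cessation, physical activity, and improved adherence to preventive medication". Section 5 (Intervention) describes it as "targeted counselling in lifestyle changes focusing on smoking cessation, everyday physical activity, and adherence to preventive medication". Cessation is thus one of three named targets.

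In section 7.1.1 smoking stands in the list introduced by "Tertiary outcomes after 12 weeks will include", in the block on behaviour change. Its measure is "Daily; weekly; Rarely; Former; Never smoked", categorical, obtained by interview.

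Section 8.3 analyses the tertiary outcomes by intention-to-treat. The test that applies to smoking is "either chi-squared test or fisher's exact test for categorical variables". It states no change from baseline, no restriction to baseline smokers and no adjustment for baseline smoking.

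Section 7.1.2 says "Before the participants are randomized following baseline data will be collected", and the list has smoking on the same five categories. It adds: "For current smokers the amount and type of tobacco is also recorded".

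Section 4.3 has no smoking criterion for entry. Section 9.3 accepts that chance imbalance is possible at this sample size and names smoking as a candidate stratification factor, but leaves that choice to the feasibility evaluation.

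**The concern.** The row sits among behaviour changes, but what it holds is a status. A participant who stops because of the counselling is recorded as *Former*, as is one who stopped decades ago. Never-smokers and baseline ex-smokers cannot quit during the trial, yet both count in the between-arm table. Any effect on quitting is therefore multiplied by the proportion who smoked at baseline, and chance imbalance in that proportion adds noise.

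At stake is how clearly the trial describes one of its three behavioural targets. The derivation is also left open. Whether *Rarely* counts as smoking, and who forms the denominator, could be settled after the data are seen.

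**Working it through.** **Plan's own figure.** The documents give no figure for smoking. The only computed sample size is 298 per group for a future blood pressure trial (section 8.1). I reproduce it to within one: 2 × (1.960 + 0.842)² × 18.3² / 4.21² ≈ 297, with the intervention-group SD in both arms. It enters below only as the size of that later trial.

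**Inputs.** From the plan: N = 40 and a 5% significance level. Assumed, because the documents do not give them: n = 20 per arm, two-sided tests, baseline current smokers p = 20-40%, former smokers 35%, and quit rates of 45% (intervention) v 20% (control). No relapse is modelled.

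**Dilution, at p = 30%.**
- Smoking at 12 weeks, intervention: 0.30 × (1 − 0.45) = 0.165.
- Smoking at 12 weeks, control: 0.30 × (1 − 0.20) = 0.240.
- Expected difference: 0.30 × 0.25 = 0.075. A 25-point quit effect becomes 7.5 points.
- Variance: 0.165 × 0.835/20 + 0.240 × 0.760/20 = 0.0160, so the SD is 12.7 points.

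**Part due to baseline imbalance.**
- Variance of the baseline difference: 2 × 0.30 × 0.70/20 = 0.0210 (SD 14.5 points).
- Its covariance with the 12-week difference: (0.55 + 0.80) × 0.21/20 = 0.01418.
- Share of variance explained: 0.01418² / (0.0210 × 0.0160) ≈ 0.60.

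Across other assumed quit rates (20% v 40%, 20% v 50%, 30% v 60%) and p = 20-40%, simulation put this share at 43-67%.

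**Direction of the observed difference at 20 per arm.** Smokers per arm are Bin(20, p), quitters Bin(smokers, quit rate), and 12-week smokers Bin(20, p(1 − quit rate)). Summing these probabilities exactly gives:

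| Baseline smokers | Status: zero or wrong | Status: strictly wrong | Quit proportion: zero or wrong | Quit proportion: strictly wrong |
|---|---|---|---|---|
| 20% | 41% | 24% | 29% | 18% |
| 30% | 35% | 21% | 21% | 16% |
| 40% | 29% | 18% | 16% | 13% |

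Independent simulations agree to about one point. Their ranges are 29-42% (strictly wrong 19-25%) for status and 16-30% (strictly wrong 12-19%) for the quit proportion.

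**Smaller effect, quit 40% v 25%, p = 30%.** Zero or wrong is 44% v 33%, and strictly wrong 29% v 27%. The gaps shrink from 14 to 11 points and from 5 to 2 points.

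**Power at 20 per arm.** Over the other assumed quit rates above, power is about 4-7% for the five-category test and 2-14% for quitting among baseline smokers.

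**If the definition were carried to 298 per arm.** With quit rates of 20% v 50%, power at 20%, 30% and 40% smokers is about 43%, 66% and 82% for the five-category test, against 92%, 98% and over 99% for quitting among baseline smokers.

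**The case against.** A reader might infer that the trial cannot show cessation, or will yield no quit proportion. The documents do not support that. The same five categories are recorded before randomisation, so quitting by arm can be derived from data already planned. The list in 7.1.1 states what is recorded and need not be the full outcome definition. A reader might also infer bias, but under randomisation the status comparison is not biased for a shift in current smoking.

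Nor can it be stated as fact that the comparison reflects pre-stroke smoking more than quitting. The share from baseline imbalance is above one half in most assumed scenarios but not all, and the documents give neither prevalence nor quit rates.

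Much of the gap in the zero-or-wrong figures is exact ties. At 30% smokers, strictly wrong results differ only by 21% v 16%. The large power gap belongs to a future trial, sized on blood pressure, whose smoking endpoint is not set here. Section 1.4 names participation rate and blood pressure variance as the planning estimates, not a quit proportion. Section 8.2 tabulates participant characteristics by arm, so an imbalance in smoking could be seen.

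All of this stands and limits the size of the point. It does not supply the missing analysis: the stated method compares status in everyone, and a better alternative is available from the same data.

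**Conclusion.** The point holds as a minor one. The specified smoking comparison is diluted and noisy, not biased, and no analysis of quitting is stated although the data for it will exist. Under the assumed inputs, using the quit proportion among baseline smokers lowers the chance of a zero or wrong-direction result by roughly 12-14 percentage points, and of a strictly wrong one by about 5-6 points. The gain is smaller if the quit effect is smaller. Neither analysis can serve as a test with 20 per arm. The outcome is tertiary in a feasibility trial whose main aims are participation and adherence, so no main conclusion changes. The definition matters more if it passes into the full-size trial.

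**What to change.** In sections 7.1.1 and 8.3, define smoking cessation as no smoking at 12 weeks among participants recorded as daily, weekly or rarely smoking at baseline. Report it descriptively as n/N per arm, with the difference and its 95% CI. Add a baseline-by-12-week cross-tabulation of the five categories per arm, which also shows relapse among baseline former smokers.

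This costs wording only, since both values are already collected. The downside is a small denominator: 20 × 0.20 = 4 to 20 × 0.40 = 8 smokers per arm. With 6 per arm and quit rates of 45% v 20%, the approximate 95% half-width is 1.96 × √(0.45 × 0.55/6 + 0.20 × 0.80/6) ≈ 51 points around a difference of 25. The result should be presented as a description, not a test.
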